#### **5.3.2** Adverse Events

The applicable definition of an Adverse Event (AE) is in the study protocol. All AEs occurring from when a subject signs informed consent to when a subject exits the study will

be accounted for in the reporting. A treatment-emergent AE is an event not present prior to exposure to treatment or any pre-existing event that worsens following exposure to treatment. All information obtained on adverse events will be displayed by subject and eye.

The number and percentage of all ocular adverse events and the associated two-sided exact 95% confidence interval, including secondary surgical interventions (SSIs) for either eye, will be tabulated for any event and by preferred term with a breakdown by overall, first eyes, and second eyes. An eye with multiple ocular adverse events of the same preferred term is only counted once toward the total of this preferred term. Adverse events related to the study IOL are referred to as adverse device effects.

Adverse events will be summarized in tables with the following:

- 1. All Adverse Events (Serious and Non-Serious Combined)
  - a. Ocular
  - b. Non-Ocular
- 2. All Adverse Device Effects
  - a. Ocular
  - b. Non-Ocular
- 3. All Serious Adverse Events (including Serious Adverse Device Effects)
  - a. Ocular
  - b. Non-Ocular
- 4. Subject Listings
  - a. Non-Serious Ocular
  - b. Non-Serious Non-Ocular
  - c. Serious Ocular
  - d. Serious Non-Ocular
  - e. Pre-Treatment Adverse Events
  - f. Ocular Adverse Events from Non-Study Eyes
  - g. Secondary Surgical Interventions

#### **5.3.3** Device Deficiencies

The number and percentage of all device deficiencies will be tabulated by overall, first eyes, and second eyes. In addition, a listing of device deficiencies will also be provided.

# **5.3.4** Problems During Surgery

The number and percentage of eyes with problems during surgery will be tabulated by overall, first eyes, and second eyes. In addition, a listing of subjects with problems during surgery will be provided.

# 5.3.5 Other Surgical Procedures During Surgery

The number and percentage of eyes with other surgical procedures during surgery will be tabulated by overall, first eyes, and second eyes. A listing of all other surgical procedures during surgery will be provided.

# 5.3.6 Monocular Best Corrected Visual Acuity (BCDVA)

The number and percentage of eyes with visual acuity of

- 1. 20/20 Snellen or better
- 2. 20/25 Snellen or better
- 3. 20/32 Snellen or better
- 4. 20/40 Snellen or better
- 5. Worse than 20/40 Snellen

will be presented at each study visit, separately for overall, first eyes, and second eyes. A listing of all monocular BCDVA results, as well as a listing of eyes with any postoperative BCDVA worse than 20/40 will be provided.

#### **5.3.7** Intraocular Pressure

Descriptive summaries (N, mean, median, standard deviation, minimum and maximum) of observed values will be presented at each study visit, separately for overall, first eyes, and second eyes.

A summary table with number and percentages of eyes in each category of IOP change from baseline to last IOP assessment and to any scheduled visit by implanted eye will be presented

according to the following categories: >30 mmHg increase, 21 to 30 mmHg increase, 11 to 20 mmHg increase, 6 to 10 mmHg increase, 5 mmHg decrease to 5 mmHg increase (no change), 6 to 10 mmHg decrease, 11 to 20 mmHg decrease, 21 to 30 mmHg decrease, and >30 mmHg decrease, separately for overall, first eyes, and second eyes. For change to any scheduled visit, an eye will be counted only once in the category that represents maximum change from baseline across all postoperative assessments.

A listing will be provided which presents all eyes with an increase or decrease in IOP of more than 10 mmHg at any visit compared to the same eye at baseline.

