# 5.2 Safety Hypotheses

There are no formal safety hypotheses in this study. The focus of the safety analysis will be a comprehensive descriptive assessment of all safety endpoints stated in Section 5.1.

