#### 9 SAMPLE SIZE AND POWER CALCULATIONS

The precision of the estimated rate can be assessed using the width of an exact two-sided 95% confidence interval. In Figure 9-1, the exact two-sided 95% confidence intervals with a sample size (N) of 3,000 are shown when the observed rate ranges from 1 to 10 (per 1,000).

As an example, with N=3,000, the width of the exact two-sided 95% confidence interval will be 3.6 (per 1,000) when the observed rate is 2 (per 1,000).

Figure 9-1 The exact two-sided 95% confidence intervals with N=3,000 when the observed rate ranges from 1 to 10 (per 1,000)

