# 12 APPENDIX

 Table 12-1
 Schedule of Study Procedures and Assessments

Procedure/ Assessment	Visit 0 (≤ 40 days pre-surgery 1st eye, ≤ 60 days pre-surgery 2nd eye)	Visit 00 & Visit 00A (surgery)	Visit 1 & Visit 1A (Day 1-2 post surgery)	Visit 2 & Visit 2A (Day 7-14 post surgery)	Visit 3 & Visit 3A (Day 30- 60 post surgery)	Visit 4 & Visit 4A (Day 90 - 180 post surgery)	UNSV
Informed Consent	X						
Demographics	X						
Patient Medical History (Ocular and Nonocular) 	X						
Medications (use of medication prior to, during and post-surgery must be documented) 	X	X	X	X	X	X	X
Inclusion/ Exclusion	X	X					
Adverse Events (Volunteered and Elicited)	X	X	X	X	X	X	X
Device Deficiencies		X	X	X	X	X	X
Subject Reported Symptoms	X		X	X	X	X	X
Best Corrected Visual Acuity (BCVA)	X		X	X	X	X	X
Intraocular Pressure	X		X	X	X	X	X
Problems during surgery		X					
Other Surgical Procedures		X					
Aqueous cell	X		X	X	X	X	X
Aqueous flare	X		X	X	X	X	X
Corneal edema	X		X	X	X	X	X
Corneal haze	X		X	X	X	X	X

Fibrin in the anterior chamber, on the surface of the iris or on the intraocular lens (IOL)	X	X	X	X	X	X
Eyelid edema	X	X	X	X	X	X
Conjunctival hyperemia	X	X	X	X	X	X
Ciliary flush	X	X	X	X	X	X
Corneal precipitates	X	X	X	X	X	X
Hypopyon	X	X	X	X	X	X
Dilated fundus examination	X	X 				
Vitreous cell	X	$X^1$	$X^1$	$X^1$	$X^1$	$X^1$
Vitreous haze	X	X 	X 	X 	X 	X1
Photo documentation		$X^2$	X 	$X^2$	$X^2$	X 
Culture of ocular media		$X^2$	$X^2$	$X^2$	$X^2$	$X^2$

 Required for cases of exacerbated post-surgical intraocular inflammation only.

- Medical History: All ocular history, targeted systemic history
- Concomitant Medications: All ocular medications, targeted systemic medications

*NOTE*: Visits with an "A" refer to visits for the 2nd eye visits for cases where both eyes of a subject are enrolled. In the eCRF these visits will be noted with wording of "2nd Eye" instead of A. For example: Visit 1A will be shown as Visit 1-2nd Eye.

 Required at certain visits for cases of exacerbated post-surgical intraocular inflammation. See Manual of Procedures for details on requirements for which visit(s) testing is required.

 Concomitant medications and medical history must be fully documented in the subject source documents. CRF data will be Targeted:

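### Does counting each eye once by its maximum IOP change, with no stated sign convention or tie rule, make the any-visit table unreliable?

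*SAP*

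**What the plan says.** SAP Section 5.3.7 plans three IOP outputs.

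- **By-visit summaries.** These cover observed values, not changes: "Descriptive summaries (N, mean, median, standard deviation, minimum and maximum) of observed values will be presented at each study visit".
- **A categorical table.** It covers "IOP change from baseline to last IOP assessment and to any scheduled visit by implanted eye". There are four bands of rise, a no-change band and four mirror-image bands of fall. The middle of the scale reads "6 to 10 mmHg increase, 5 mmHg decrease to 5 mmHg increase (no change), 6 to 10 mmHg decrease, 11 to 20 mmHg decrease". For the any-visit part, "an eye will be counted only once in the category that represents maximum change from baseline across all postoperative assessments".
- **A listing.** It shows "all eyes with an increase or decrease in IOP of more than 10 mmHg at any visit", relative to the same eye's baseline.

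Section 5.1 places IOP among the other safety endpoints. Section 5.2 states no formal hypotheses and describes the aim as a "comprehensive descriptive assessment of all safety endpoints stated in Section 5.1". In Table 12-1 the "Intraocular Pressure" row is marked at baseline, at all four postoperative visits and in the unscheduled-visit column.

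**The concern.** A single maximum is clear on a one-directional grade, such as the worst-case grades in Sections 5.3.10 to 5.3.13. On a scale that runs both ways it is not, for three reasons.

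1. The maximum could be the largest signed value or the largest absolute value.
2. On the absolute reading, an eye at +8 and later -8 mmHg fits two rows and no rule chooses between them. An eye at +8 and later -9 appears only as a fall.
3. The part is described as change to any scheduled visit, but the maximum runs over all postoperative assessments. IOP is also measured at unscheduled visits.

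The other outputs do not fully make up for this. The by-visit summaries show no changes, the last-assessment part misses changes that have resolved, and the listing starts above 10 mmHg. Two programmers could therefore produce different tables from the same data, and some transient changes of 6 to 10 mmHg would appear in no change output.

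**Working it through.** Section 5.3.7 states no figure to reproduce. The check first applies the rule to patterns and then asks how many eyes could be affected.

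**Patterns.** Each eye below is within 5 mmHg of baseline at its last assessment.

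| Changes (mmHg) | Absolute reading | Signed reading | Listed? |
|---|---|---|---|
| +8, rest within 5 | 6 to 10 rise | 6 to 10 rise | no |
| -9, rest within 5 | 6 to 10 fall | no change | no |
| +8, -9 | 6 to 10 fall | 6 to 10 rise | no |
| +8, -8 | tie | 6 to 10 rise | no |
| -15, +3 | 11 to 20 fall | no change | yes |

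Take whole-mmHg patterns with a largest rise and a largest fall both between 6 and 10, and other visits at 0. There are 5 × 5 = 25 of these. The absolute reading displaces the rise in 10, displaces the fall in 10 and ties in 5. An eye that moves 6 mmHg or more in one direction only is always placed correctly. These are counts of patterns, not expected frequencies of eyes.

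The signed reading would put an eye in a row for falls only if every postoperative value were a fall of at least 6 mmHg. That would nearly empty four of the nine rows, so the layout itself argues against it.

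**Frequency (all inputs assumed, since the SAP gives no IOP mean, SD or correlation).** Changes at four visits are normal and rounded to whole mmHg, with 400,000 simulated eyes per setting. The Day 1 change has mean 0, 1.5 or 3 and SD 4, 5 or 6. The later changes have mean -2, -1 or 0 and SD 3. The correlation between changes is 0, 0.3 or 0.5. The middle setting is Day 1 mean 1.5 and SD 5, with later mean -1. Eye counts use the 3,300 eyes of Section 1.2. In the displaced shares, ties are assigned to the rise.

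| Correlation | 0 | 0.3 | 0.5 |
|---|---|---|---|
| Eyes moving 6 or more both ways, per 1,000, middle setting | 48 | 15 | 4.4 |
| Same, of 3,300 eyes | 157 | 50 | 14 |
| Same, per 1,000, all settings | 22 to 113 | 4 to 55 | 0.5 to 26 |
| Rises of 6 or more displaced, all settings | 2.0% to 11.3% | 0.6% to 3.7% | 0.1% to 1.4% |
| Falls of 6 or more displaced, all settings | 5.5% to 24.5% | 1.6% to 13.8% | 0.3% to 7.5% |

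For example, 4.4 per 1,000 × 3,300 = 14.5 eyes.

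A correlation above 0 is the more plausible case, because every change subtracts the same baseline. If baseline and postoperative readings were independent with equal variance s², two changes would have covariance s² and variance 2s² each, so the correlation would be s²/2s² = 0.5.

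In the middle setting, about 72% to 73% of the eyes moving both ways have a masked change that neither the last-assessment part nor the listing shows. At correlation 0.5 that is 0.73 × 14.5 ≈ 11 eyes, or 11/3,300 = 0.3%. At correlation 0 it is 0.72 × 157 ≈ 113 eyes, or 3.4%. Exact ties make up 23% to 36% of the eyes moving both ways. At correlation 0.5 that is 0.36 × 14.5 ≈ 5 eyes. Assigning all ties to the rise raises the share of falls displaced: at the middle setting with correlation 0.5 it is 1.9%, or about 1% if ties are left out. A masked change of 11 mmHg or more occurs in under 1 eye per 1,000 in every setting, and the listing covers such eyes.

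**The case for a change.** The strongest case for a change is that the SAP writes this rule itself, writes it loosely, and could repair it in a sentence or two with no new data. Separate blocks for each eye's largest rise and largest fall would need no tie rule and would lose nothing. Section 5.3.6 asks for a listing of all visual acuity results, whereas Section 5.3.7 asks for no full IOP listing, so a reader could not recover a masked change. On the least favourable assumptions the share of falls displaced is not trivial.

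Part of this stands. The sign convention, the tie rule and the place of unscheduled readings are indeed unstated, and the wording could be tighter. The rest is weaker:

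- The high shares need zero correlation between changes that share one baseline.
- A table that counts each eye once shows the distribution of each eye's largest change, and the SAP says openly that this is what it does. It does not claim to count every eye that ever rose or ever fell. The two-block layout answers that different question, and its rows would no longer sum jointly to 100%.
- On unscheduled visits, the opening words of the sentence can be read as limiting what follows to scheduled visits. The listing covers any visit, so a change above 10 mmHg at an unscheduled visit is shown either way.

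**Conclusion.** The concern describes the wording correctly but does not call for a change to the plan. The symmetric bands, and a listing that treats rises and falls alike, point to largest absolute change. An analyst would adopt that reading, and would settle ties and unscheduled readings in the table specifications before database lock. On that reading the table is a fair single-count summary. What it leaves out is the smaller of two opposite movements in the same eye, mostly of 6 to 10 mmHg.

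The likely number is small: about 11 of 3,300 eyes in the middle setting at correlation 0.5, with well under 1% of rises and about 1% to 2% of falls displaced. It would be larger if changes were less correlated, up to about 113 eyes in the same setting at correlation 0. All of these figures rest on assumed IOP distributions. None of them touches the inflammation rates of Section 5.1, a hypothesis test or a decision, and changes above 10 mmHg are listed whichever convention is used.

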# **5.3.8** Slit Lamp Observations

For each slit-lamp parameter, number and percentages of eyes that experience an abnormality will be presented by overall, first eyes, and second eyes by scheduled visit. A listing will be provided which presents all eyes with an abnormality in any slit-lamp parameter at any postoperative visit.

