#### 5 SAFETY ANALYSIS STRATEGY

# 5.1 Safety Endpoints

The primary safety endpoint is the rate (per 1,000 IOL implants) of post-surgical intraocular inflammation (based upon the specified case definition) reported within a 180-day post-surgical period following attempted implantation of study IOLs for Cohort 2.

The secondary safety endpoints are the rates (per 1,000 IOL implants) of Toxic Anterior Segment Syndrome (TASS), acute postoperative endophthalmitis, chronic postoperative endophthalmitis, and uncategorized cases of post-surgical intraocular inflammation (based

upon the specified case definition), respectively, reported within a 180-day post-surgical period following attempted implantation of study IOLs for Cohort 2.

Other safety endpoints for Cohort 2 are:

- Adverse events
- Device deficiencies
- Problems during surgery
- Other surgical procedures during surgery
- Best Corrected Distance Visual Acuity (BCDVA)
- Intraocular Pressure (IOP)
- Slit lamp observations that include, but not limited to:
  - o Hypopyon
  - Corneal precipitates granulomatous
  - o Corneal precipitates non-granulomatous
  - o Fibrin in the anterior chamber, on the surface of the iris or on the IOL
- Fundus observations
- Slit lamp examinations
  - o Aqueous cell
  - Aqueous flare
  - Eyelid edema
  - Conjunctival hyperemia
  - Ciliary flush
- Corneal Assessment
  - Corneal edema

- Corneal haze
- Evaluation of vitreous cells
- Evaluation of vitreous haze
- Culture of ocular media
- Subject Reported Symptoms

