#### 5.3.11.2 Corneal Haze

The number and percentage of "worst case" by grading for corneal haze at scheduled postoperative visits will be presented by overall, first eyes, and second eyes. A listing of eyes with a rating greater than the lowest level (Rating 0 – clear cornea) at any visit will be provided.

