# **5.3.15** Subject Reported Symptoms

The number and percentage of subject reported symptoms at each scheduled visit will be presented by overall, first eyes, and second eyes. A listing of subject reported symptoms will be provided for the subset of eyes with post-surgical intraocular inflammation.

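### Several sign and symptom tables count scheduled visits only, so a finding seen solely at an unscheduled visit enters no percentage (minor reporting gap)

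*SAP*

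**What the plan says.** Section 5.1 names slit lamp observations as a safety endpoint ("Slit lamp observations that include, but not limited to" hypopyon, two kinds of corneal precipitates, and fibrin), alongside fundus observations, corneal edema, corneal haze and subject reported symptoms.

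The tables planned for these items are tied to scheduled visits:

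- Section 5.3.8, slit lamp observations: "number and percentages of eyes that experience an abnormality will be presented by overall, first eyes, and second eyes by scheduled visit". Section 5.3.9 uses the same rule for fundus observations.
- Section 5.3.11.1, corneal edema: one combined table by scheduled postoperative visit.
- Section 5.3.11.2, corneal haze: worst-case results "by grading for corneal haze at scheduled postoperative visits will be presented by overall, first eyes, and second eyes".
- Section 5.3.15, symptoms: "The number and percentage of subject reported symptoms at each scheduled visit will be presented by overall", and by first and second eyes.

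The listings are mostly wider. Section 5.3.8 lists "all eyes with an abnormality in any slit-lamp parameter at any postoperative visit", and Section 5.3.9 does the same for fundus. For haze, "A listing of eyes with a rating greater than the lowest level (Rating 0 – clear cornea) at any visit will be provided"; edema has a matching any-visit listing. Symptoms are listed only for eyes with post-surgical intraocular inflammation.

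Table 12-1 has an unscheduled-visit (UNSV) column next to the scheduled windows.

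**The concern.** Section 5.2 states that the study tests no hypotheses and that its safety analysis is a comprehensive description of the endpoints in Section 5.1. The descriptive tables are therefore the result, not a supplement to a test.

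For the items above, data are collected at unscheduled visits and then left out of the percentages. For similar signs, such as aqueous cell and flare, the SAP uses an any-visit rule, and it gives no reason for the difference. Two things are at stake:

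- A finding seen solely at an unscheduled visit contributes to no tabulated percentage.
- By-visit columns cannot be added up to give the number of eyes ever affected, because one eye may appear at several visits. A reader who wants that number must count it from a listing, and for symptoms the listing is incomplete.

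**Working it through.** **1. The rules side by side**

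| Item (SAP section) | Table counts | Listing covers | Marked under UNSV in Table 12-1 |
|---|---|---|---|
| Hypopyon, fibrin, corneal precipitates (5.3.8) | scheduled visits | any postoperative visit | yes |
| Fundus (5.3.9) | scheduled visits | any postoperative visit | not readable* |
| Corneal edema (5.3.11.1) | scheduled visits | any visit | yes |
| Corneal haze (5.3.11.2) | scheduled visits | any visit | yes |
| Symptoms (5.3.15) | scheduled visits | eyes with inflammation only | yes |
| Aqueous cell, flare, eyelid edema, conjunctival hyperemia, ciliary flush (5.3.10) | worst case, any postoperative visit | any postoperative visit | yes |
| Vitreous cells, eyes with inflammation (5.3.12) | worst case, any postoperative visit | any postoperative visit | yes, inflammation cases only |

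*In the text available, the marks in the dilated-fundus row cannot be matched to columns, so nothing is claimed about fundus data at unscheduled visits.

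The first five rows have the narrower table rule and the last two the wider one. Only the symptoms row lacks a listing that covers all eyes.

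**2. Can a finding fall between scheduled visits?**

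The windows in Table 12-1 are Day 1-2, Day 7-14 ("Visit 2 & Visit 2A (Day 7-14 post surgery"), Day 30-60 and Day 90-180.

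- Days inside a window: 2 + 8 + 31 + 91 = 132.
- Days of 1-180 outside every window: 180 − 132 = 48, made up of Days 3-6 (4), 15-29 (15) and 61-89 (29); 4 + 15 + 29 = 48.

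A sign that appears and clears within one of these gaps can be recorded only at an unscheduled visit. This shows that the situation is possible, not how often it occurs.

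**3. Is there a size?**

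The SAP's one computed figure is in Section 9: width 3.6 per 1,000 for the exact 95% interval at 2 per 1,000 with N = 3,000. With 6 events in 3,000 the Clopper-Pearson limits are 0.734 and 4.348 per 1,000, width 3.614, so the figure reproduces. The present point does not depend on it.

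Purely as an illustration, assume a sign occurs in 6 of 3,000 eyes and that k of the 6 show it only at unscheduled visits. An any-visit table shows 6/3,000 = 2.00 per 1,000. The scheduled-visit tables together can show at most (6 − k)/3,000 × 1,000:

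- k = 0: 2.00
- k = 1: 1.67
- k = 3: 1.00
- k = 6: 0

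Nothing in the SAP narrows k, or says how often any of these signs occurs. The range is the whole of what is possible, not an estimate.

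**The case against.** The strongest reply is that a by-visit table is correct for what it reports. The SAP defines no cumulative rate for these signs or symptoms, so no stated estimate is biased. Unscheduled visits happen at varying times in a selected subset of eyes and fit no visit column. That stands, and it is why the remedy is an additional column rather than a change to the existing ones.

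Other parts of the reply also stand:

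- The primary and secondary rates in Section 5.3.1 count events reported within 180 days, whatever the visit type.
- The listings recover slit-lamp, fundus, edema and haze findings from any visit. With few affected eyes, a reader could count from them.
- Symptoms that qualify as adverse events enter the Section 5.3.2 tables, which run from consent to exit. Adverse events are collected at unscheduled visits.
- Section 5.3.11.1 also plans the inflammation rate by presence of corneal edema. That could imply a count of eyes ever with edema, but the SAP does not say which visits define presence.
- Section 5.3.10 does not name unscheduled visits. Its wording covers them on a plain reading, and Section 5.3.7 shows that the SAP can say scheduled when it means that.

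A reader might infer more than the document supports. One inference is that every sign *first* seen at an unscheduled visit is lost; in fact, a sign still present at the next scheduled visit is counted there. Another is that acute inflammation tends to present at unscheduled visits, so the tables are biased downward for the key cases; the SAP says nothing about when inflammation presents, and it does not contain the case definition. A third is that 48 of 180 days measures what is missed; it does not, because days inside a window are not continuously observed either.

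What survives is the unexplained difference between sections, the lack of an any-visit percentage, and the hole for symptoms.

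**Conclusion.** The point holds as a minor weakness in descriptive reporting. The tables in Sections 5.3.8, 5.3.9, 5.3.11.1, 5.3.11.2 and 5.3.15 omit findings seen solely at unscheduled visits, and none is specified as a count of eyes ever affected. This is inconsistent with Sections 5.3.10 and 5.3.12. The only information that reaches neither a table nor a listing of its own kind is symptoms reported at unscheduled visits by eyes without inflammation.

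No size of undercount can be derived from the SAP. No endpoint rate, confidence interval or conclusion in it changes. The verdict rests on two readings: that any postoperative visit in Sections 5.3.10 and 5.3.12 includes unscheduled ones, and that the UNSV marks in Table 12-1 mean the data are recorded there.

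**What to change.** In Sections 5.3.8, 5.3.9, 5.3.11.1, 5.3.11.2 and 5.3.15, keep the scheduled-visit columns and add one column headed *any postoperative visit, including unscheduled*:

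- Count each eye once: highest recorded grade for graded items (corneal edema and haze), any occurrence for ungraded ones (slit-lamp and fundus abnormalities, and each symptom).
- Use as denominator the safety-set eyes with at least one postoperative assessment of the item.
- For corneal edema, take the highest grade over locations as well as visits, so that records from before and after 15 November 2021 can be combined.
- State in Section 5.3.10 that its any-visit rule includes unscheduled visits.

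The symptom column closes the hole for eyes without inflammation, so the symptom listing need not be extended.

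The cost is a few lines of SAP wording and one column per table. No new data are needed. The count in the new column cannot be lower than in any single scheduled-visit column, so the reported numbers may rise slightly.
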